PROTOCOL TITLE: Effects of Perampanel on Neurophysiology Test Perimeters

PRINCIPAL INVESTIGATOR: [name] Weill Cornell Medicine

IRB Protocol #: 1704018150

ClinicalTrials.gov Identifier: #NCT03653741

Current Version 6/1/2018

Prior Version Dates:

Version December 8, 2017

BACKGROUND

Neurophysiology tests such as EEG, VEP, BAER, and SEP are used to evaluate the functional status of the neuroaxis from the periphery all the way to the cortex. Many anti-epileptic drugs have been shown to affect these tests. Anti-epileptic medications such as phenytoin, carbamazepine, and oxcarbazepine have been shown to cause background slowing on EEG. Anti-epileptic medications have also been shown to prolong latency values in VEP, SSEP and BAER. One small study demonstrated that the AMPA receptor antagonist talampanel was associated with dose-dependent increase in beta activity. To date, there have been no published data on whether FDA approved anti-epileptic medication perampanel (same mechanism of action as talampanel) affects EEG, VEP, SSEP, or

BAER. As for anticipated side effects of perampanel, in a small study of 6 patients that received a single dose of perampanel at 6mg (the dose we will be using), the most common side effects was headache, fatigue, somnolence, and dizziness.

STUDY DESIGN

We hypothesize that perampanel, a FDA approved drug for epilepsy, will affect commonly performed neurophysiology tests: electroencephalogram (EEG), somatosensory evoked potential (SEP), brainstem auditory evoked potential (BAEP), and visual evoked potential (VEP). More specifically, we hypothesize it will decrease background frequency content in EEG and increase latency in VEP, SEP, and BAEP. We plan to recruit 12 healthy normal male subjects. All subjects will have VEP, SSEP, EEG, and BAER performed before and 1 hour (when Cmax is reached) after receiving 6mg of perampanel. Subjects will also receive a blood draw 1 hour after ingestion of perampanel for serum perampanel level for correlation with any changes seen in the neurophysiology test data. There is no placebo nor randomization. Subject's participation concludes after completion of post-perampanel ingestion neurophysiology tests.

Primary: Quantify the effects of perampanel on electroencephalography, visual evoked potential, somatosensory evoked potential, and brainstem auditory evoked potential to guide interpretation of test results for patients taking perampanel.

Secondary: 1) Correlate effects on neurophysiology test perimeters with known drug side effects. 2) Pinpoint where in neuroaxis perampanel exerts maximal effects, which may shed light on where it exerts its anti-seizure effects.

Based on similar studies, we will recruit 12 subjects. Each subject will undergo 4 neurophysiology tests. Then each subject will ingest perampanel and then repeat the 4 neurophysiology tests. We will compare the pre-ingestion to the post-ingestion values in the 4 tests using a Wilcoxon signed-rank test, which is more appropriate for small samples than a standard paired t-test. We do not expect any dropouts, but if they occur we will perform sensitivity analysis by providing results for different imputed values for the dropouts.

INCLUSION AND EXCLUSION CRITERIA

Healthy subjects between the ages of 18 to 50 years old with a body mass index of 19-29 kg/m² will be recruited. Subjects would be excluded if they use recreational drugs and have any neurologic disease, psychiatric condition or any other condition that may affect outcome and risk subject safety.

Furthermore, anyone that would not be able to participate in neurophysiology tests will also be excluded. Subject will also be excluded should they take any over the counter medication or consume caffeine or alcohol 12 hours prior to the study.

DATA AND SAFETY MONITORING PLAN

The risk to subjects is minimal risk for all tests involved. Blood levels of perampanel will be drawn 1 hour after drug administration. Additionally, the 4 tests (VEP, EEG, SEP, BAEP) will be completed both prior to and following study drug administration. This study does not have interim and complete stopping rules. This is a small study and we do not expect to encounter any major adverse events since the tests we will be administering is well tolerated and the study drug, perampanel, is FDA approved and well tolerated in the way we will be administering it (single dose at 6mg). We do not expect any adverse events that would stop a subject's participation. The subject can withdraw voluntarily. The risk of taking perampanel to the subject is classified as greater than minimal risk. In a small study looking at single dose of perampanel administered to healthy volunteer at 6mg, the reported side effects were headache, dizziness (excluding vertigo), somnolence, and fatigue. These were all classified as mild to moderate in severity. Rate of side effect was reported as 16.8% while placebo was 12.6%. Serious Side Effects: Perampanel may cause new or worse aggressive behavior, homicidal thoughts or threats, hostility, anger, anxiety, irritability, being suspicious or distrustful (believing things that are not true), and other unusual or extreme changes in behavior or mood. You should contact the study doctor immediately should you experience any of the above. Antiepileptic drugs, including perampanel, may cause suicidal thoughts or actions in a very small number of people, about 1 in 500. Study subjectss should call their healthcare providers right away if they have any of the following symptoms, especially if they are new, worse, or worrisome: thoughts about suicide or dying, thoughts of self-harm, attempt to commit suicide, new or worse depression, new or worse anxiety, feeling agitated or restless, panic attacks, trouble sleeping (insomnia), new or worse irritability, acting aggressive, being angry or violent, acting on dangerous impulses, an extreme increase in activity and talking (mania), and other unusual changes in behavior or mood. You should call your study doctor immediately if you notice any changes in mood, ideas or behavior. Most common side effects: Dizziness, fatigue, sleepiness, irritability, falls, nausea, imbalance, gait problems, vertigo, and weight gain. Less commonly seen side effects: Headache, anxiety, upset stomach, vomiting, constipation, urinary tract infection, problems with coordination, rash, bruises, muscle pain, blurry vision, swelling of arms/legs, numbness, memory problems, confusion, euphoria, low blood sodium level, increase triglyceride level, skin laceration, pain in extremities, back pain, and head trauma. Additional Risks: The U.S Drug Enforcement Agency (DEA) may classify some, but not all, medicines as controlled substances. Perampanel has been classified as schedule III. Medicines in this category have an approved medical use but have potential for abuse, physical dependence, or psychological dependence. The risk is lower compared to drugs in Schedule I and II. Some other anti-epileptic medicines have also been listed as controlled substances. It is possible that perampanel may interact with other medicines and herbal supplements that you are taking. Before starting the study, your study doctor will determine that you are not taking anything that can interact with perampanel. During the collection of blood samples, you may experience slight discomfort and a small amount of bleeding, discoloration or bruising at the site where the needle was inserted. Clot formation and infections may occur at the puncture site, but this is extremely rare. Fainting may occur during or

shortly after having blood drawn. If faintness is experienced, you should lie down immediately to avoid possible injury caused by falling and notify the site study staff. The total amount of blood taken during the study is approximately 40-60 teaspoons. Reproductive Risks: Perampanel does not affect the ability of men to father children.

Subjects will be monitored during the tests and interviewed in order to detect any adverse events. An investigator will be with the subject at all times to recognize and record any adverse events. Since the study involves only one dosing of study drug, there will not be any negative impact on subjects resulting from study closure or a subject being terminated from the study. Adverse events will be rated mild, moderate, or severe. Adverse events will be reported to the IRB and to Eisai (study sponsor). Aside from the IRB, unexpected adverse events will also be promptly reported to Eisai. The principle investigator will be monitoring the safety of the subjects.

Interim analysis will not be needed as drug is FDA approved and small study so analysis will be done after completion of all subject. Data safety monitoring board is not needed since drug is FDA approved and will be administered only once to normal subjects. It is found to be generally well tolerated in this condition.

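### The objectives credit perampanel with a pre-to-post change that a single-arm, fixed-order comparison cannot separate from time or repeat testing

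*Protocol*

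**What the plan says.** Under STUDY DESIGN the protocol describes one group of 12 healthy men. Each has EEG, visual, somatosensory and brainstem auditory evoked potentials recorded, takes 6 mg of perampanel, and has the same tests again at 1 hour. The order is the same for everyone, and the text states: "There is no placebo nor randomization".

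The stated comparison is: "We will compare the pre-ingestion to the post-ingestion values in the 4 tests using a Wilcoxon signed-rank test". A serum level is also drawn at 1 hour, to be correlated with any changes in the test data.

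The primary objective is to "Quantify the effects of perampanel on electroencephalography, visual evoked potential, somatosensory evoked potential, and brainstem auditory evoked potential to guide interpretation of test results", with patients on the drug in mind. The second secondary objective is to "Pinpoint where in neuroaxis perampanel exerts maximal effects, which may shed light on where it exerts its anti-seizure effects". The expected direction is given in advance: "More specifically, we hypothesize it will decrease background frequency content in EEG and increase latency in VEP, SEP, and BAEP".

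Under INCLUSION AND EXCLUSION CRITERIA there is one restriction that limits non-drug variation: "Subject will also be excluded should they take any over the counter medication or consume caffeine or alcohol 12 hours prior to the study".

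The protocol does not say whether latencies and EEG frequency are computed by software or scored by a person.

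**The concern.** The single-arm design is disclosed, and naming a direction in advance is good practice. Neither is at fault. The difficulty is the step from the comparison to the claim. The null hypothesis of the signed-rank test is that values do not shift between the first and second round. The objectives read a shift as the action of perampanel. Time spent in the session and the repetition of the tests also lie between the two rounds, and nothing in the design separates them from the drug.

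The results are meant to inform how clinicians read these tests in patients taking perampanel. Any non-drug shift would pass into that guidance in full. If such shifts differed between the four tests, the ranking used to find the site of greatest effect would be distorted as well.

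A further route exists if a person scores the recordings. A reader who knows which recording came after the dose also knows the answer the hypothesis expects.

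**Working it through.** **What the comparison estimates.** For one parameter in subject i, write

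post − pre = δ + τ + e,

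where δ is the drug effect, τ is the average shift from time and repeat testing, and e is subject-level variation. The paired comparison estimates δ + τ, and the test addresses δ + τ = 0. It speaks to δ alone only if τ = 0. No drug-free repeat is planned, so τ cannot be estimated.

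**The two partial safeguards.**
- *Serum level.* A correlation between change and level is unaltered when the same constant τ is added to every subject's change. A clear correlation would support drug involvement, but it neither reveals nor removes τ. With one level per subject at a single dose there is no observation at zero exposure, and extrapolating to zero would need an assumed shape.
- *12-hour exclusions.* These limit some sources of variation carried in from before the session. They do not act on what changes within it.

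**Size, for illustration.** The protocol gives no significance level, SD, effect size or test-retest figure, so there is no stated calculation to reproduce.

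Input from the protocol: n = 12, signed-rank test.

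Assumptions: two-sided 0.05; no drug effect (δ = 0); differences scaled to SD 1; τ set to 0, 0.1, 0.25 or 0.5 SD.

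*Exact null distribution.* There are 2^12 = 4,096 equally likely sign patterns.
- Rank sum ≤ 13: 87 patterns, so 2 × 87/4,096 = 0.0425.
- Rank sum ≤ 14: 107 patterns, so 2 × 107/4,096 = 0.0522, which exceeds 0.05.

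The test therefore rejects when the smaller rank sum is 13 or less, with true size 4.2%.

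*Simulated rejection rate (1,000,000 runs per case; no-shift row exact):*

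| Non-drug shift τ | Normal | t(5) | Uniform |
|---|---|---|---|
| 0 | 4.2% | 4.2% | 4.2% |
| 0.1 SD | 5.2% | 5.6% | 5.1% |
| 0.25 SD | 10.7% | 13.0% | 9.5% |
| 0.5 SD | 31.5% | 38.8% | 26.6% |

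*Estimation.* The Hodges-Lehmann estimate, with τ = 0.5 SD and δ = 0, averages 0.500 SD. It is wrong by the whole of τ, and more subjects would not reduce that. The matching signed-rank interval covers the true drug effect with probability 1 − rejection rate. For normal differences:
- no shift: 1 − 0.042 = 95.8%
- 0.25 SD: 1 − 0.107 = 89.3%
- 0.5 SD: 1 − 0.315 = 68.5%

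**The case against.** The strongest reply is that an objective names a question and is not a conclusion. The protocol is candid about its design, never claims that the signed-rank test separates drug from time, and plans an exposure correlation that bears on attribution. Every shift size above is assumed, and 0.1 SD is negligible. The rewording alters no data and no estimate, so the caveat could be made when results are reported.

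Much of this stands. The document does not contradict itself about its design, and the percentages are not evidence that a shift exists. What does not stand is that the matter can wait. The objectives already name the drug as the cause and set a clinical use for the result, and no analysis plan can supply the missing control. The serum correlation deserves credit, but a shift common to all subjects leaves it unchanged.

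Three stronger readings are tempting, and the documents support none of them.
- *That recordings are hand-scored by unmasked readers.* The protocol does not say how values are extracted. Reading procedures may be set out in an analysis plan or laboratory procedure not shown, so silence here is not a defect.
- *That drift affects mainly the EEG and so biases the search for the site of action in a known direction.* Nothing in the protocol says how drift differs between tests.
- *That the placebo symptom rate in the section on safety monitoring shows how large a non-drug shift would be.* Those figures (16.8% on drug, 12.6% on placebo) are side-effect reports from another study and say nothing about latencies or EEG frequency.

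**Conclusion.** The point holds as a mismatch between what the objectives claim and what the design can identify. The comparison supports a statement about change from before to after a single dose. It does not support an unqualified statement about the effect of perampanel or where that effect is greatest.

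This conclusion needs no assumed number: any non-drug shift common to the subjects enters the estimate in full, at any sample size. How much it matters in practice is unknown. On the stated assumptions it ranges from negligible at 0.1 SD to about 31% false positives per parameter at 0.5 SD (27% to 39% with the other two distributions tried).

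The masking element is conditional and applies only to measures that a person scores. The design can stand as it is; the inference should be restated before results are reported.

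**What to change.** 1. Word the primary objective, the second secondary objective and the planned conclusion as pre-to-post change after a single dose in healthy men. State in each that time and repeat-testing effects are not separated from the drug.
2. State which latencies and EEG frequencies are fully computed; these need no masking. For any that a person scores, remove the pre/post labels, code the files, have current staff score them in random order, and lock the readings before decoding. The reason is that the hypothesis tells a reader which direction to expect.

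The cost is a change of wording plus file coding for any hand-scored measures. No subject, session, arm or staff member is added. The downsides are slightly slower reading and a more modest claim. Masking removes only reader expectation. Drift is disclosed by the rewording and remains in the estimates.

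### Secondary objective 2 asks where in the neuroaxis the effect is largest, but the separate pre/post tests that the protocol states cannot show this, and their outcomes share no common scale

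*Protocol*

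**What the plan says.** All of this is in the protocol; no statistical analysis plan is shown.

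- **Objective.** STUDY DESIGN, secondary objective 2: "Pinpoint where in neuroaxis perampanel exerts maximal effects, which may shed light on where it exerts its anti-seizure effects".
- **Rationale.** BACKGROUND says that neurophysiology tests "evaluate the functional status of the neuroaxis from the periphery all the way to the cortex".
- **Outcomes.** STUDY DESIGN gives a directional hypothesis, that the drug will "decrease background frequency content in EEG and increase latency in VEP, SEP, and BAEP". It does not say which peaks are read, or whether latency is absolute or interpeak.
- **Analysis.** The paragraph after the secondary objectives reads: "We will compare the pre-ingestion to the post-ingestion values in the 4 tests using a Wilcoxon signed-rank test".
- **Other analyses named.** Changes are to be correlated with serum level, and effects with known side effects. Neither compares one level of the neuroaxis with another.
- **Size.** "Based on similar studies, we will recruit 12 subjects".

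**The concern.** To say that an effect is maximal at one site is to say that it is larger there than elsewhere. The stated analysis instead asks four separate questions, each whether one test changed between the two recordings. A reader who wants a site from those four answers has to rank them somehow, and the protocol supplies neither a contrast nor a scale for doing so.

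The two obvious rankings both mislead. Ranking by p-value favours the test with the least noise. Ranking by raw size of change favours the test with the largest numbers or the most noise, and frequency cannot be ranked against milliseconds at all. If absolute peak latencies are used, there is a third problem: a delay early in a pathway is carried into every later peak, so levels beyond the true site also look affected.

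At stake is a secondary conclusion. The study could name a site when the drug acts equally at all of them, or name the wrong one. The primary objective, quantifying the effect on each test, is not affected.

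**Working it through.** **1. The plan's own figure.** The only relevant figure is n = 12. It rests on precedent, with no alpha, power, effect size or SD, so it cannot be reproduced. Working backwards with an assumed two-sided alpha of 0.05 and 80% power, the detectable standardised change is (1.960 + 0.842)/√12 = 2.802/3.464 = 0.81 by the normal approximation. With the exact Wilcoxon test (3,000 simulated runs), power is 68% at 0.81 and 80% at 0.93.

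**2. Objective against analysis.** Write δ_j for the true change in test j. The stated tests address δ_j = 0 for each j separately. The objective needs δ_a − δ_b for pairs of sites. No such difference is tested.

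**3. Reproducibility.** Inputs: n = 12, an identical true shift of 2 in all four tests, the exact Wilcoxon test and 2,000 runs. The SDs of change are assumptions; the protocol gives none.

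| Assumed SDs of change | Most reproducible test has smallest p | Noisiest test has largest mean change |
|---|---|---|
| 2, 2, 2, 2 | each test 24% to 26% | each test 23% to 27% |
| 2, 2.5, 3, 4 | 52% | 32% |
| 1, 2, 3, 4 | 87% | 34% |

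No site is truly maximal in any row, so each share should be about 25%. With unequal SDs, the p-value ranking follows reproducibility strongly, and the raw-change ranking leans the other way.

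**4. Units.** Assumed baselines, not in the protocol: EEG 10 Hz, VEP 100 ms, SEP 20 ms, BAEP 5.6 ms. The same 5% change reads as 0.5 Hz, 5 ms, 1 ms and 0.28 ms. A uniform 2% slowing of the three latencies gives 2.0, 0.40 and 0.112 ms. The largest to smallest ratio is 2.0/0.112 = 17.9, which is simply 100/5.6. It illustrates scale and predicts nothing about the drug.

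**5. Upstream delay, only if latencies are absolute.** The latency at level k is the sum of segments 1 to k. A delay d in segment 1 adds d to every level, while the interval between two later peaks is (later + d) − (earlier + d), which is unchanged. Simulated with n = 12, 2,000 runs and independent segments, a true delay of 1 in segment 1 only, and assumed SDs of change of 1, 0.3 and 0.3:

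| Scoring | Significant at levels 1, 2, 3 | Correct level has largest mean change |
|---|---|---|
| Absolute latency | 85%, 82%, 79% | 39% |
| Segment (interpeak) latency | 85%, 5%, 3% | over 99% |

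**6. What a paired contrast could detect.** Let each of two segments have SD of change σ, with correlation ρ between them. The SD of their difference is σ√(2(1 − ρ)). Taking 0.93 from step 1, the difference detectable with 80% power is:

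- ρ = 0.5: 0.93 × 1.00σ = 0.93σ
- ρ = 0: 0.93 × 1.41σ = 1.32σ
- ρ = −0.5: 0.93 × 1.73σ = 1.61σ

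Negative values are plausible because adjacent intervals share a peak, so a reading error at that peak lengthens one interval and shortens the other.

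**The case against.** The strongest reply is that much of this concerns analyses the protocol never states. It does not say that latencies are absolute, that there is one per test, or that sites will be ranked by milliseconds or by p-value. Interpeak intervals and central conduction time fit the word latency, and the choice of peaks is commonly left to a statistical analysis plan, which may exist. The magnitudes above rest on assumed baselines and SDs.

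Most of that is right and limits the point. The upstream-delay argument is conditional on absolute latencies. A reader might infer that the objective would name a site whatever the data show, but the text does not support this: no ranking rule is given, and four null results could simply name none. A reader might also infer that the visual pathway will look about 18 times more affected than the brainstem. That follows only from the assumed latencies and only if raw milliseconds are compared across modalities, which the protocol does not propose. Nor is the anti-seizure clause a fault. It is already hedged and needs no change.

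One part of the reply fails. The protocol does state both its comparative objective and its analysis of effect, and that analysis does not answer the objective. This is a mismatch within the document, not merely a detail left for later.

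**Conclusion.** The point holds in a limited form. Objective 2 is comparative, and the one analysis of effect that the protocol states is a set of separate pre/post tests on outcomes without a common scale. A maximal site inferred from them could reflect units or reproducibility and, if absolute latencies are used, an upstream delay. The documents support could, not would.

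Under the assumed unequal SDs, the most reproducible of four equally affected tests leads on p-value in 52% to 87% of runs, where 25% would be fair. With absolute latencies and a delay in the first segment only, the correct level shows the largest mean change in 39% of runs, against over 99% with interpeak intervals. These figures show direction and possible scale; different SDs would change them. The matter deserves correction but is confined to a secondary objective.

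**What to change.** For objective 2, measure within-pathway intervals on the traces already recorded: BAEP I-III and III-V, and SEP peripheral-to-cervical and cervical-to-cortical. State in advance the scale on which change is expressed. Name a maximal site within a pathway only if a paired within-subject contrast between levels supports it.

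Label any ranking across modalities (EEG and VEP against SEP and BAEP) as exploratory. Percent change removes the units but does not correct for unequal reproducibility, and interpeak intervals give no matching quantity for EEG or VEP.

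The cost is a few sentences and a few extra readings per trace, with no new procedure or visit. The downside is that with 12 subjects the contrast detects only large differences between levels (step 6 of the working), so the honest answer may be that no level can be distinguished.

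### Could the eligibility section, as worded, let in women or healthy recreational drug users?

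*Protocol*

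**What the plan says.** Three parts of the protocol bear on who may enter.

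- **Study Design** fixes the population and the comparison: "We plan to recruit 12 healthy normal male subjects", each tested before and after a single dose. It adds: "There is no placebo nor randomization".
- **Inclusion and Exclusion Criteria** opens with "Healthy subjects between the ages of 18 to 50 years old" and a body mass index range, without mentioning sex. The main exclusion follows: "Subjects would be excluded if they use recreational drugs and have any neurologic disease, psychiatric condition or any other condition that may affect outcome". Its closing words bring in the subject's safety. Of two further exclusions, one concerns recent intake, "Subject will also be excluded should they take any over the counter medication or consume caffeine or alcohol 12 hours prior to the study", while the other covers people unable to undergo the tests.
- **Data and Safety Monitoring Plan** adds a check on other substances, "Before starting the study, your study doctor will determine that you are not taking anything that can interact with perampanel", and gives its reproductive-risk statement for men only: "Perampanel does not affect the ability of men to father children".

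**The concern.** Eligibility text is applied person by person, so screening staff should be able to use it without inference. Two features of this section seem to fall short.

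First, someone working from the eligibility section alone would find that a healthy woman in the stated age and body mass index ranges meets every criterion listed there. She would nevertheless fall outside the design, and the reproductive-risk text does not address women.

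Second, the main exclusion links drug use to the list of conditions with *and*. As a strict logical statement, both must be present before anyone is excluded. Coffee on the morning of the study would then disqualify a subject, while recreational drug use alone would not.

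What would be at stake is the make-up of a 12-subject before-and-after comparison of nervous-system recordings. With no control group, a subject whose recordings shifted for reasons other than perampanel would be hard to recognise.

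**Working it through.** The point concerns wording, and the protocol attaches no figure to it. The check is therefore to compare the passages and then ask what could reach the analysis.

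**1. Sex.** Study Design says men. The reproductive-risk statement speaks of men. The eligibility section says healthy subjects and is silent on sex. The last is broader than the first two but compatible with them, since every healthy man in range is a healthy subject in range. No sentence admits women. Read as a whole, the protocol recruits men only, and the shortfall is that a restriction stated once is not repeated a few paragraphs later.

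**2. The exclusion sentence under each reading.** Let D be recreational drug use and C any listed condition.

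- Literal reading: exclude if D and C. A subject with neurologic disease who takes no drugs (C without D) is not excluded by this sentence. Nor is a healthy user (D without C).
- List reading: exclude if D or C. Both are excluded.

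The first result under the literal reading shows that it cannot be what was meant. A study of healthy normal volunteers would not write an exclusion for neurologic disease that applies only to drug users. The requirement to be healthy would still keep that subject out, but the sentence would then do almost no work of its own. Recreational drugs are named because their use is meant to exclude.

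**3. Other text bearing on a healthy user.**

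- The requirement to be healthy covers people with a condition, but not clearly a user without one.
- The exclusion for inability to undergo the tests does not mention drugs.
- The 12-hour rule names over-the-counter medication, caffeine and alcohol only.
- The catch-all for other conditions could be applied to drug use that bears on both the recordings and safety.
- The check on interacting substances is worded to cover anything that interacts with perampanel, although the sentence before it speaks of medicines and herbal supplements. It would catch some users but is not a general exclusion.

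On the strictest reading, then, a gap remains for a healthy user whose drug neither interacts with perampanel nor is treated as a relevant condition.

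**4. What could reach the analysis.** The planned comparison is a Wilcoxon signed-rank test on within-subject differences, dᵢ = postᵢ − preᵢ. If past drug use shifts a subject's recordings by a constant amount sᵢ, then (postᵢ + sᵢ) − (preᵢ + sᵢ) = postᵢ − preᵢ, and the shift cancels. This assumes that the shift is additive. What does not cancel is an effect that changes between the two recordings, or one that alters the response to perampanel. The protocol gives neither the chance that such a subject is admitted nor the size of such an effect, so no bias can be computed and none is shown.

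**The case for a change.** The best case for a change is that the defect sits in the section that exists to define who may be dosed. The protocol says of the drug: "The risk of taking perampanel to the subject is classified as greater than minimal risk". It also reports that perampanel is a Schedule III substance with abuse potential, and it has no stopping rules. Recreational drug use is therefore a relevant screening item on the protocol's own account, and the 12-hour limit on caffeine and alcohol shows that recent intake was thought to matter. The repair would take two sentences and leave the endpoint, analysis and sample size alone.

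Part of this stands. The wording is looser than eligibility text should be, the sex criterion would be better placed with the other criteria, and no sentence expressly closes the gap for a healthy user on the strict reading.

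The step to a consequence does not stand. It requires an investigator to adopt a reading that defeats the sentence's evident purpose, or to apply the eligibility section while ignoring the recruitment statement under Study Design. Nothing in the protocol says that screening rests on that one paragraph alone. The protocol's reasons for having no data safety monitoring board do not help the case either: they include regulatory approval and single dosing as well as normal subjects, and do not turn on how this exclusion is phrased.

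**Conclusion.** No change to the plan follows. The eligibility section omits a restriction stated under Study Design, and its main exclusion is loosely joined, but both are clerical slips that a sensible investigator resolves in the intended way. Under that reading the same subjects are enrolled with or without cleaner wording, so the effect on the enrolled population, the stated figures and the analysis is nil.

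This rests on two assumptions: that the exclusion is applied as a list of separate grounds, and that the male-only statement governs recruitment. If the first failed and a healthy user were enrolled, a stable additive effect on the recordings would cancel within subject. Only a changing effect, or an altered response to perampanel, would matter, and the protocol gives no basis for sizing either. If the protocol is amended for another reason, repeating the sex criterion and separating the exclusions would be reasonable tidying. Whether a condition must threaten both outcome and safety in order to exclude is a separate question for the sponsor and is not decided here.
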